would preclude their participation and remove any metal on their person. They will complete pre-drug mood questionnaires and then ingest a dose (0, 0.4 or 0.8 g/kg ethanol) under double blind conditions and be placed in the scanner. Subjects will complete questionnaires rating their subjective state every 5 min, using a key pad. Heart rate will be recorded manually from the scanner control room every 2 min. BAL will be measured immediately after the scan. The fMRI scan is expected to take 60 min. After the scan they will be escorted to the HBPL until BAL levels return to 0.04 g%, and where they will complete final self-report ratings, physiological indices. After completing all three experimental sessions, the senior investigator will explain the purpose of the study. Participants will be told that the drug they received was alcohol and they will be paid \$300. If subjects drop out before completing all three sessions they will receive \$25 for each session completed.

Alcohol dose preparation

Alcohol and placebo will be administered in individual servings of black cherry sugar-free jello (Weafer et al, 2016). The doses of 0.4 and 0.8 g/kg ethanol are equivalent to 2 or 4 standard drinks, and are expected to yield BAL's of 40 and 80 mg/100 ml. The effects are expected to peak within 20 min. Alcohol will be administered in jello to mask the taste (Ralevski et al., 2006) and for fast consumption and absorption. The alcohol jello will be prepared with 3 parts 95% alcohol and 5 parts of water, mixed together with the jello powder and then refrigerated overnight. Placebo jello will be prepared with 8 parts of water. Participants will receive jello servings (5 g alcohol each) in black opaque 2 oz cups. The number of servings required to reach a dose of 0.8 g/kg alcohol will be determined for each participant based on body weight. Placebo will be administered in an equivalent number of jello servings.

fMRI Data Acquisition and Analysis

fMRI experiments will be performed using a 3T GE MRI scanner in the MRIRC. During the fMRI scan, the subject will be positioned supine inside the bore of the magnet and the head will be immobilized using padding. A 32 channel_head coil will be used. A T2*-weighted gradient-echo echo-planer imaging (EPI) pulse sequence (TE (echo time) = 30ms; TR (repetition time) = 2000ms; flip angle = 70 degree; image matrix = 64 x 64; FOV (field of view) = 20cm x 20cm) will be used for functional scan.

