EPI images will be processed and analyzed using AFNI (Cox 1996), FSL5.0.9 (FMRIB Software Library), and SPM12 (Wellcome Trust Centre for Neuroimaging). The time series will be volume registered to the median image to reduce motion artifact using 3dvolreg within AFNI. Motion outliers will be identified and censored from analyses. Subjects will be excluded if at least one of their scans showed motion >10mm total displacement in any one direction or if more than 50% of volumes within any time point window (see below) were censored. fMRI analyses. Imaging data will be temporally downsampled to the behavioral data by taking a windowed average including the 35 time points before and after the time of the subjective response measurement, resulting in a downsampled dataset at the same temporal resolution as the behavioral data. We chose this relatively long time period because subjective responses are slow-changing, and averaging over a larger window allow for better signal to noise ratio. The windows do not overlap for any time point. The downsampled fMRI data will be voxel wise correlated with the subjective response data (across all time points) using AFNI's 3dfim+, with the resultant coefficients converted to z-scores using Fischer's transformation. The correlation maps will then be coregistered to the participant's anatomical data and warped to MNI space, resampled to 2mm isotropic voxels and smoothed with an 8 mm FWHM isotropic Gaussian kernel.

Further analyses will follow the plan we used in our previous study (Weafer et al, 2019). We compared correlation maps between the time course of subjective response ratings and the time course of BOLD signal following alcohol to those following placebo using paired *t*-tests. In order to control for typical alcohol consumption, we entered average drinks per week

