responders, selecting individuals who report the largest and smallest increases on selfreported Arousal (Profile of Mood States). We anticipate some dropouts because of scheduling issues, illness, movement artifact during scanning and other technical problems. The subjects will participate in three scanning sessions, at least 3 days apart. Each scanning session will consist of an oral dose of alcohol (0, 0.4 or 0.8 g/kg), and a 60-min fMRI scan with resting state BOLD and ASL acquisition sequences.

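### A single failed scan, or a single failed window of about 2.3 min, removes the whole participant from the BOLD analysis, although each paired comparison needs only two of the three scans

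*Combined protocol and SAP*

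**What the plan says.** The rule stands in the image-processing paragraph of fMRI Data Acquisition and Analysis. It has two triggers. The first is gross movement: "Subjects will be excluded if at least one of their scans showed motion >10mm total displacement in any one direction". The second is heavy censoring: "or if more than 50% of volumes within any time point window (see below) were censored". In both, the participant is the unit removed.

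A window is a "windowed average including the 35 time points before and after the time of the subjective response measurement", and the acquisition has "TR (repetition time) = 2000ms". Ratings come every 5 min (Experimental Procedure: "Subjects will complete questionnaires rating their subjective state every 5 min, using a key pad"), and the plan notes that "The windows do not overlap for any time point".

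The Design section plans three scans per person (0, 0.4 and 0.8 g/kg) in 15 stimulant and 15 sedative responders. The analysis text describes paired t-tests between an alcohol and a placebo condition in four regions of interest, each at p < 0.0125. The closing Summary expects some dropouts, among other reasons from "movement artifact during scanning and other technical problems", but gives no rate.

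The documents describe no exclusion at scan or window level, no sensitivity analysis for the motion rule, no replacement of excluded participants, and no reporting of exclusions by dose or responder group.

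**The concern.** The unit that is damaged and the unit that is removed do not match. Movement spoils a window or a scan, but the rule removes a person. A paired comparison of one alcohol dose with placebo does not use the scan at the other dose, so a failure there has no bearing on whether that pair is valid. Likewise, a within-session correlation between ratings and BOLD signal can still be computed when one window is missing.

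Two things are at stake. The first is precision: there are only 30 scanned participants, tested at a Bonferroni-adjusted level, and usable scans are thrown away. The second is who remains. Potential risks lists restlessness and shakiness or tremor among the effects of alcohol, and participants are chosen for the character of their response to it. Movement could therefore differ by dose or by responder group. Under a participant-level rule, such a difference at one dose would carry over into comparisons that do not involve that dose.

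**Working it through.** The plan gives no power calculation, effect size, dropout rate or motion-failure rate, so it has no figure of its own for this rule. Two related figures can be checked and both agree: 0.05/4 = 0.0125, and the windows indeed do not overlap (step 1).

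**1. Length of a window and the trigger**
- Width: 35 + 35 = 70 volumes, or 71 with the centre. At 2 s each this is 140-142 s, about 2.3 min.
- Spacing: 300 s / 2 s = 150 volumes, so windows of 70-71 volumes cannot overlap.
- More than 50% of 70 or 71 volumes means at least 36 volumes, or 36 × 2 = 72 s of censored data.

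**2. Number of windows per participant**
- Ceiling: 60 min / 5 min = 12 per session, or 36 over three sessions.
- The closing Summary says the hour holds both BOLD and ASL. One ASL run under ASL Analysis takes 35 × 2 × 4.7 s = 329 s, about 5.5 min. The number of BOLD windows is not stated. I use 24 to 36 per participant (8 to 12 per session) as an assumed range.

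**3. Scan trigger**

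Assumptions: one scan per session, the same failure probability *p* for each scan, independent failures, and the paired test applied to each alcohol dose against placebo. Participants kept under the current rule: 30(1−p)³. Complete pairs for one contrast if only the failed scan is dropped: 30(1−p)². Usable scans discarded by the current rule: 90(1−p) − 90(1−p)³.

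| Assumed p | Participants kept, current rule | Pairs per contrast, scan-level exclusion | Usable scans discarded (of 90 acquired) |
|---|---|---|---|
| 5% | 25.7 | 27.1 | 8.3 |
| 10% | 21.9 | 24.3 | 15.4 |
| 15% | 18.4 | 21.7 | 21.2 |

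**4. Power**

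Two-sided paired t-test, noncentral t, alpha 0.0125, assumed standardized paired difference (dz) 0.5, n rounded to whole participants. With all 30, power is 54%.

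| Assumed p | Current rule | Scan-level exclusion | Difference, points |
|---|---|---|---|
| 5% | n = 26: 46% | n = 27: 48% | 2 |
| 10% | n = 22: 37% | n = 24: 42% | 4 (37.3% to 41.6%) |
| 15% | n = 18: 28% | n = 22: 37% | 9 |

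**5. Window trigger**

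Share of participants lost with *m* independent windows, each failing with probability *q*: 1 − (1−q)^m.
- q = 1%, m = 24: 1 − 0.99²⁴ = 21%.
- q = 1%, m = 36: 1 − 0.99³⁶ = 30%.

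If failures cluster within person, the same 1% falls on fewer people. With a beta-binomial model, m = 36 and an assumed within-person correlation of 0.05, 0.1 or 0.2, the loss is 19%, 14% or 9%.

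**6. Illustration of unequal loss**

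Assume 20% scan failure at 0.8 g/kg in one responder group and 5% in the other, with 5% at the remaining two conditions in both.
- Kept under the current rule: 15 × 0.95 × 0.95 × 0.80 = 10.8 against 15 × 0.95³ = 12.9.
- Pairs for 0.4 g/kg against placebo under scan-level exclusion: 15 × 0.95² = 13.5 in both groups.

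This shows the mechanism only. The documents contain no movement data by dose or group.

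**The case against.** The strongest defence is that a prespecified complete-case rule keeps the same people in every contrast and is simple to apply. The plan also works to limit movement with a mock scan, head padding and custom pads. The 10 mm limit is loose: in-plane voxels are 200/64 = 3.125 mm, so 10 mm is 3.2 voxels. The threshold for a motion outlier is not defined, so the rule may rarely bite. All of this stands, and it limits what can be said about frequency. It does not justify discarding intact scans when the rule is triggered.

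Four stronger readings are tempting, and the documents do not support them.

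- **A large loss of power.** A reader might take 1% independent window failure with 36 windows, get 21 of 30 participants, and find that an effect detectable with 80% power at n = 30 (d = 0.645) now has 59%. That compares the rule with losing nobody. It also uses the maximum number of windows and ignores clustering. For failed scans, the proper comparator also loses the contrast that needed the scan, and the recoverable gain is the 2 to 9 points above.
- **Selective removal of the responders the trial chose.** Both stimulant and sedative responders are chosen, and the list of side effects includes drowsiness as well as restlessness and tremor. Neither direction nor size can be established.
- **A rule carried over from a two-condition study.** The text ties only the further analyses, described after the rule, to the earlier study. It does not say where the rule came from.
- **Loss of all data from a participant.** The rule stands in the BOLD paragraph. Nothing says that ASL or questionnaire data are dropped as well.

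**Conclusion.** The concern holds for the BOLD analysis. As written, one scan over the limit, or about 72 s of censored volumes inside one window, removes up to three sessions, including scan pairs that the planned comparisons could use. Given the same failures, the participant-level rule can never keep more data than exclusion of the damaged unit.

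The practical size is unknown because it rests wholly on assumed failure rates. For scan failures of 5-15% it is modest to moderate. For window failures it could be larger, but the estimate depends heavily on the number of windows and on clustering. Unequal loss by dose or responder group is a possibility that the plan should be able to detect; it is not a demonstrated bias. With 30 participants, movement losses already expected and a cheap remedy, the change should be made.

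**What to change.** - **Window:** drop a window when more than 50% of its volumes are censored.
- **Session:** drop a session when that session exceeds the motion limit or keeps fewer than a prespecified minimum number of windows. The investigators should set and justify that minimum before analysis, once the number of BOLD windows per session is fixed. The threshold for a motion outlier should be stated at the same time.
- **Participant:** keep the other sessions in every contrast they can support, either as available pairs or in a mixed model on session z-scores with a participant random effect. Do not weight sessions by the number of windows minus 3. That weight assumes independent windows, and the plan itself describes the ratings as slow-changing.
- **Reporting:** tabulate dropped windows and sessions by dose and responder group, and report the current participant-level rule as a sensitivity analysis.

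The cost is SAP wording and some extra analysis; no new data are needed. If the mixed model is chosen, it replaces the paired t-tests in the region-of-interest analysis, and the SAP must say separately how the SPM12 whole-brain analysis handles missing sessions. There are small downsides: contrasts may rest on slightly different participants, sessions contribute unequal numbers of windows, and dropping windows near peak effect can change what the within-session correlation measures. Scan-level exclusion also does not remove selection from the contrast whose own scan failed, which is why the tabulation and the sensitivity analysis are needed.

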number of subjects. More recently, a study used fMRI to show that oral alcohol suppressed brain activity during performance of simple cognitive tasks (Horn et al. 2006). However, few studies have examined the localized effects of alcohol in the brain in relation to its self-reported subjective effects. As noted above, we recently (Weafer et al, 2018) examined fMRI BOLD response after intravenously administered alcohol. As expected, we found that alcohol produced stimulant-like effects in a subset of individuals, and using region of interest analyses we showed that the time course of stimulation correlated with BOLD signal in the striatum. In the present study we aim to extend this finding i) using more naturalistic, oral administration of ethanol, ii) using two different doses of alcohol, and iii) adding ASL measures to monitor changes in blood perfusion to inform interpretation of neural activation changes. We hypothesize that inter-individual variation in the self-reported subjective effects are expected to be associated with increases in the mesolimbic system (related to dopamine activity), whereas sedative-like effects are expected to be more associated with areas rich in GABA.

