Design: We will measure individual differences in brain activity after two doses of alcohol (0.4 g/kg, 0.8 g/kg) or placebo using fMRI. Participants (N=50) will first be pre-selected ('ascertained') based on their responses to a single dose of alcohol (0.8 g/kg) in the behavioral laboratory. Individuals who exhibit either a clear stimulant-like response or a clear sedative-like response to alcohol will be invited to continue to the three fMRI scanning sessions. From the 50 participants tested, we will select 15 stimulant responders and 15 sedative responders. The three imaging sessions will be at least 72 h apart. At each session, subjects will receive the beverage containing alcohol or placebo, and then be placed in the fMRI scanner. Order of the three drug conditions (0, 0.4 and 0.8 g/kg ethanol) will be randomized and the drug will be administered under double-blind conditions. Immediately before and after the scan, subjects will complete standardized questionnaires to assess mood and subjective drug effects. We hypothesize that stimulant-like subjective effects will be associated with increases in activation in the striatum and regions related to the mesolimbic dopamine circuit. To minimize variability related to body composition and cycle phase, only males will be recruited for this preliminary study. Later, we will extend the study to include female participants.

Subject Recruitment and Screening

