At the orientation session subjects will read and sign the consent form, which outlines the procedures and lists the classes of drugs subjects might receive and their possible effects. Participants will be informed that they might receive a placebo, stimulant/anorectic, sedative/tranquilizer, opiate/analgesic, alcohol or a cannabinoid/marijuana-like drug. This use of mild deception in this study is necessary to prevent expectancy effects. Subjects will be told the purpose of the study is to investigate the effects of psychoactive drugs upon brain activation. In the consent form subjects agree not to use any drugs except for their normal amounts of caffeine for 24 hours before and 6 hours following each session, and not to operate any machinery requiring concentration for 6 hours following the sessions. They will also agree to fast for 4 hours prior to each session. Participants will also practice completing the questionnaires to be used in the study. They will be allowed to view the fMRI scanners, undergo a mock scan and be instructed on the imaging procedures which will be employed. We will query subjects about any prior history of claustrophobia or anxiety in small spaces. Each subject will complete a detailed questionnaire regarding the presence of any metal implants or metal objects in their body.

Experimental Procedure:

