from the TLFB as a covariate. Based on previous associations between subjective alcohol response and striatal activity, we focused our analyses within three hypothesis-driven anatomically-focused bilateral striatal regions of interest (ROIs): the nucleus accumbens, caudate, and putamen. We also included bilateral primary visual cortex to serve as a negative control ROI. The striatal ROIs were defined via the AAL atlas and created using MARINA (www.bion.de/eng/MARINA.php; Walter *et al*, 2003). The primary visual cortex ROI (Brodmann area 17) was created using the WFU PickAtlas tool (Maldjian *et al*, 2004; Maldjian *et al*, 2003). We extracted parameter estimates/ β weights representing the correlation between BOLD signal and subjective ratings in z-scores from each ROI following alcohol and placebo and conducted paired *t*-tests in SPSS to compare the two drug conditions. We applied a Bonferroni correction across the four ROIs tested, and so the p-value was set at p < 0.0125. We also conducted exploratory, whole-brain analyses of correlations between BOLD signal and stimulation and sedation ratings using SPM12 (cluster-forming voxel-wise height of *p* < 0.001, *k* = 50). Statistical inferences were based on cluster level significance, corrected for family wise error (FWE, *p* < 0.05).

ASL Analysis

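### Does the paired test of Fisher-z correlations mislead if ratings simply vary more on alcohol than on placebo?

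*Combined protocol and SAP*

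**What the plan says.** The section on fMRI data acquisition and analysis sets out two steps. First, BOLD is averaged in windows around each rating, and the averaged series "will be voxel wise correlated with the subjective response data (across all time points"; the coefficients are then Fisher-transformed. Second, following the group's previous study, correlation maps are compared "following alcohol to those following placebo using paired" t-tests. The values extracted from each region of interest (ROI) are called parameter estimates or β weights, but are described as "representing the correlation between BOLD signal and subjective ratings in z-scores", so they are correlations and not unstandardised slopes. The ROIs are nucleus accumbens, caudate and putamen, plus a control: "We also included bilateral primary visual cortex to serve as a negative control ROI". Bonferroni over four ROIs gives p < 0.0125. Exploratory whole-brain analyses cover "correlations between BOLD signal and stimulation and sedation ratings".

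On what the test is meant to show, the Background reports of the earlier intravenous study that "we showed that the time course of stimulation correlated with BOLD signal in the striatum". The Design section hypothesises that "stimulant-like subjective effects will be associated with increases in activation in the striatum".

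The documents plan no report of rating spread by condition, no slope analysis, and no rule for a session in which the ratings never change.

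**The concern.** A correlation mixes two things: the BOLD change per unit of rating, and the spread of the ratings relative to BOLD noise. The plan expects striatal coupling to be non-zero. If ratings rise and fall on alcohol but stay nearly flat on placebo, the alcohol correlation will be larger even when the BOLD-rating relationship is the same in both sessions. A reader told that coupling is stronger on alcohol could take this as a change in the relationship itself.

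The visual-cortex control would not reveal it. If that region is unrelated to ratings, as a negative control presumes, rating spread cannot move its z. A session with constant ratings adds a loose end, since r is then undefined.

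**Working it through.** **Stated figure.** 0.05 / 4 = 0.0125, as the plan says.

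**Inputs from the documents.** 15 + 15 = 30 scanned subjects; ratings every 5 min over a 60-min scan, so 60 / 5 = 12 points; TR 2 s; windows of 35 volumes each side, so 71 × 2 s = 142 s, shorter than the 300 s between ratings. Windows therefore do not overlap, as stated.

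**Assumed.** Rating SDs, slopes and noise are not given. The model is BOLD = b × rating + noise of unit variance, with b = 0.016, 0.025 or 0.0375 per mm and, unless noted, the same b in both conditions. A two-sided test is assumed.

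**Closed form.** ρ = b·s / √(b²s² + 1), where s is the within-session rating SD.

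| b | ρ at s = 20 | ρ at s = 10 | difference in z |
|---|---|---|---|
| 0.016 | 0.32/√1.1024 = 0.305 | 0.16/√1.0256 = 0.158 | 0.315 − 0.159 = 0.155 (from unrounded values) |
| 0.025 | 0.50/√1.25 = 0.447 | 0.25/√1.0625 = 0.243 | 0.481 − 0.247 = 0.234 |
| 0.0375 | 0.75/√1.5625 = 0.600 | 0.375/√1.1406 = 0.351 | 0.693 − 0.367 = 0.326 |

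So z moves with spread alone, as feared.

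**How often the z test rejects with equal slopes** (simulation, 6,000 replicates per cell, α = 0.0125; the three values are for the three slopes):

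| Rating SD, alcohol v placebo | z test rejects |
|---|---|
| equal | 1.1-1.4% |
| 20 v 17 mm | 3%, 5%, 10% |
| 20 v 10 mm | 27%, 65%, 95% |
| 20 v 10 mm in 15 subjects, 10 v 10 mm in the other 15 | 5%, 13%, 26% |

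A separate run of the 20 v 10 mm row gave 25%, 65% and 94%. With zero coupling and 30 pairs, the test rejects in 1.25-1.45% of trials for spread ratios from 1 to 3, so it holds its level.

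**Would a slope comparison settle the matter?** The natural addition is to compare unstandardised slopes and to add a caveat when z is significant but the slope is not. The useful check is how often that pattern appears under each explanation, at 20 v 10 mm:

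| Truth | z significant, slope not |
|---|---|
| equal slopes | 25%, 65%, 93% |
| alcohol slope b, placebo slope b/2 | 53%, 68%, 35% |

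At weak coupling the pattern is commoner when the slope truly differs. At middle coupling it is uninformative. Only at strong coupling does it point the right way. In the second row slope power is 11%, 27% and 65%, against 63%, 97% and 100% for z.

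Slopes also have biases of their own under equal true slopes:

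- Rating error of 10 mm at 20 v 10 mm makes the slope test reject in 7%, 17% and 42% of trials.
- If alcohol scales the BOLD signal and noise by 1.2 or 1.4 at equal rating SDs, the slope test rejects in 3-20% or 12-70%, while z stays at 1.1-1.6%.

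**The case for a change.** The strongest case for a change is that the striatal ROI comparison is the central test, that a drug-placebo contrast is exactly where ratings may move more on drug, and that half the scanned subjects are chosen for the greatest stimulant response. Reporting rating SDs would cost almost nothing and would show whether the issue matters in these data. The algebra stands, and so does the point that a clean visual-cortex result gives no reassurance here.

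What does not stand is the step from there to a defect. The percentages at unequal SDs are error rates only if the target is the slope, and the plan does not set that target. If alcohol moves ratings and striatal BOLD together, a higher correlation on alcohol fits the stated hypothesis. The spread difference may also be modest. Subjects are blinded, and "Participants will be informed that they might receive a placebo" or one of several drug classes; the other half of the sample is chosen for the least stimulant response; and the in-scanner items on liveliness and sluggishness could drift on placebo during an hour lying still. The handling of constant ratings may be in the earlier study's plan, which the documents adopt but which was not available here. If it is not, counting such sessions and stating how they entered the test is a gap any competent analyst would fill.

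**Conclusion.** The concern is arithmetically right but calls for no change. Followed as written, the plan supports the conclusion that the alcohol and placebo correlations differ, which is what it tests and is consistent with its hypotheses. It would not by itself show that BOLD change per unit of rating differs, and the documents do not claim that it would.

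The size cannot be fixed from the documents. With equal slopes, rejection runs from about 1% at equal rating SDs to 95% at twice the spread with strong coupling, and every value between rests on assumed SDs, slopes and noise.

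A slope analysis is a matter of preference. It is sensitive to rating error and BOLD gain, and it often fails to separate the two explanations, so a statistician could reasonably decline it. Giving rating SDs by condition beside the z results, and describing a significant result as a difference in correlation, is sound reporting that needs no amendment.
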